Effect of different neuromuscular training modalities on postural stability in healthy recreation people: A randomised controlled trial

February 19, 2024

Title: Effect of different neuromuscular training modalities on postural stability in healthy recreation people: A randomised controlled trial

Brief Title: "Neuromuscular Training & Postural Stability"

Acronym: STABLEFIT

Study Overview

Brief Summary

Background: Postural stability (PS) is a vital function that helps maintain equilibrium during standing still, locomotion, and any activities requiring high balance performance. Under static and dynamic conditions, PS is a fundamental factor for the quality of movement in everyday activities or sports. PS and adaptive ability are required in sports due to the interactions between the sensory and motor systems, which regulate postural adjustments by processing information from the visual, vestibular, and somatosensory systems, as reported by previous studies. The interest in using different exercises and protocols for improving PS in sports and physiotherapy has grown in the last few decades. Experts have proposed various training modalities to increase neuromuscular stability, balance, postural control, and general stability.

Dynamic Neuromuscular Stabilization (DNS) is a complex of correction exercises with a neuromuscular approach based on improving breathing, fundamental movements, and principles of developmental kinesiology.

Whole body vibration training (WBV) is a neuromuscular training approach that has recently become very popular among researchers and practitioners in health and sport. It is usually used as an additional method in a conventional training routine.

Designing the training program to achieve the optimal benefits for PS in healthy young adults is important in general personal health management. Although different training protocols have improved PS and general stability in everyday activities, there is still considerable debate regarding the optimal exercise modalities within an exercise program.

Aim: The purpose of this study is to determine the effects of dynamic neuromuscular stabilisation (DNS), whole-body vibration (WBV), and a combination of DNS and WBV (MIX) training modalities on postural stability (PS) in healthy recreation participants.

Method and materials: 180 gender-balanced groups were divided into four groups: MIX, DNS, VIBRO, and CONTROL, and underwent two months of treatment. The single and double-leg Center of Force (COF) parameters were collected on the Forceplate.

Detailed Description

Study design

The purpose of this study is to determine the effects of dynamic neuromuscular stabilisation (DNS), whole-body vibration (WBV), and a combination of DNS and WBV (MIX) training modalities on postural stability (PS) in healthy recreation participants. The study presents an Interventional study to improve postural stability, and the main objective is prevention. The study model is parallel with four groups.

Participants

The randomised, controlled interventional trial enrolled a gender-balanced group of 180 healthy young participants. The initial sample of respondents was recruited through an open online application that lasted two months (from 10.2.2022. to 10.4.2022.) (n=250), after which the first selection of respondents was started (n=230). Recruitment was completed after the optimal sample of subjects was filled (15.4.2022). The study sample was divided using stratified randomisation into the MIX group (n = 58), DNS group (n=57), VIBRO (n=57), and CONTROL group (n=58). At the end of the experimental program, the final sample was 180 (MIX=45; DNS=45; VIBRO=44; CONTROL=43). When stratifying, researchers use proportionate sampling to maintain the correct proportions of genders in every group. After explaining the experimental protocol, each subject provided written informed consent before participating in the study, per the Declaration of Helsinki and the Novi Sad University Human Research Ethics Committee guidelines (ethical approval number: 46-06-04/2020-1). The interventional program was conducted from 25.4.2022. to 25.6.2022.

[figure not shown]
Ethics committee – commission for implementation of scientific project research

The exclusion criteria were:

- history of neurological or musculoskeletal disorders;
- clinical conditions that could impair balance (motor disorders, medical conditions like diabetes, heart disease, stroke, issues with vision, thyroid, nerves, or blood vessels).

The inclusion criteria for this study were:

- the absence of injuries in the past six months
- the absence of other medical conditions, including COVID-19
- no programmed physical activity in the past three months.

Testing procedures

The testing was conducted at the Faculty of Sport and Physical Education, University of Novi Sad, Serbia. All participants were tested in the morning before their training session in indoor environmental conditions (temperature: 18–21°C; relative humidity: 40–60%). Before starting a performance task, general information about the examinees was recorded, including gender, age, height, and mass. Participants were instructed to wear minimal clothing and remove all footwear for height and mass measurements. In addition, they were required to eat and drink sparingly and void their bladder/excrete as needed before presenting for assessment. A stadiometer (0.1 cm accuracy, SECA Instruments Ltd, Hamburg, Germany) is used for height and mass measurements as a secondary outcome. Initial testing was conducted on 20.4.2022 and final on 25.6.2022.

Static PS was assessed with a laboratory-grade 0.5 m Footscan® plate (RSscan International, Lammerdries, Belgium) with 4096 sensors and a scanning rate of up to 300 Hz. The subject performed an individual single and double-leg task with three trials, each lasting 30 seconds with a two-minute break between each trial. During the double-leg stance test, participants were instructed to maintain an upright and as still as possible posture. They were asked to stand in their natural, comfortable position with their eyes open and fixed on a cross positioned at approximately eye level on a blackboard situated 5 meters away. Participants stood barefoot with their feet placed shoulder-width apart on a platform, and their arms were kept by their sides. Each participant was required to maintain this stable posture, and measurement started after 10 seconds (preparation period to avoid transient effects). During the single-limb stance test, participants were instructed to balance on one foot. This foot was positioned to point directly forward, aligning with reference lines in the frontal and sagittal planes. The swinging leg was flexed at the hip and knee joints to approximately 90 degrees while both arms hung naturally and relaxed at their sides. Participants were further instructed to maintain as steady a posture as possible, focusing their gaze straight ahead on a point situated 65 centimetres away on the wall. The order of testing between the left and right legs was randomised. Each participant was required to maintain this stable position, and measurement started after 5 seconds (preparation period to avoid transient effects).

Tests for static PS were the gold standard in measuring balance and were used to obtain biomechanical parameters of static PS (Hass et al., 2008). All measurements were performed in triplicate, and the mean score was retained for subsequent evaluations and analyses. The sequence of performing the balance tasks was randomised.

The software calculated the single and double-leg Sway Area (cm^2), Center of Force (COF) travelled way (mm), Medio-Lateral (ML) displacement (mm), and Anterior-Posterior (AP) displacement (mm) as primary outcomes. The following protocol was chosen based on their varying difficulty and common use as stated in previous research and is cited as reliable (Bauer et al., 2008; Springer et al., 2007; Troester et al., 2018; Verhagen et al., 2005).

Interventions

Dynamic neuromuscular stabilisation group (DNS)

DNS group's protocol involved 5 min a moderate intensity warm-up, 40 minutes of DNS movements according to the DNS approach(Frank et al., 2013), different diaphragmatic breathing, mobility and controlled movement exercises and 5 minutes of cool-down. Exercises gradually increased in complexity and difficulty level regarding DNS training principles (Mahdieh et al., 2020). The participants were instructed to refrain from engaging

in high-intensity anaerobic or anaerobic resistance training throughout the study period to prevent potential disruptions in the study results.

Whole body vibration group (VIBRO)

WBV was performed on the Power Plate Next Generation vibration platform (Power Plate North America, Chicago, IL). All training routines were approximately 50 minutes long, commencing with 5 minutes of moderate-intensity warm-up and concluding with a cool-down period. The program consisted of 8-10 static and dynamic exercises for PS that progressively increased in difficulty and complexity. During the training process, the frequency increased from 20 to 35 Hz in the last week of the experiment; the exercise duration was from 20 – 60 seconds (in the previous week), followed by 1-minute seated rest. Moreover, the complexity and difficulty of exercise increased over the experimental period. The resting period between sets was constant from the start to the end of the training process. During the experiment, the WBV intervention group performed three weekly training sessions. The participants were advised to avoid participating in high-intensity anaerobic or anaerobic resistance training during the study to ensure that it would not interfere with the study's outcomes—no changes to trial outcomes after the trial commenced. Principles and basic procedures were adapted from previous research (Fort et al., 2012; Jordan et al., 2005; Piecha et al., 2014; Torvinen, Kannu, et al., 2002; Torvinen, Kannus, et al., 2002).

Dynamic neuromuscular stabilisation with whole body vibration group (MIX)

During the two months, participants in the MIX group performed training consisting of 3 weekly sessions. The protocol consisted of a 50-minute exercise program with a 5-minute moderate-intensity warm-up and cool-down period per training session. The structural core of training included 20 minutes of WBV and 20 minutes of DNS training. Both protocols followed the previous research and training recommendations and were performed with less time and sets. Exercises with VIBRO were performed on the Power Plate Next Generation vibration platform (Power Plate North America, Chicago, IL). The program consisted of 6-8 exercises (static and dynamic) for balance and PS. Exercise progressively increases by the level of difficulty. During the training process, the frequency was also increased from 20 to 35 Hz in the last week of the experiment; the duration of exercise from 20 – 60 seconds (in the previous week), followed by 1-minute seated rest. The resting period between sets was constant from the start to the end of the training process. To prevent any interference with the study's results, participants were recommended to abstain from engaging in high-intensity anaerobic or anaerobic resistance training throughout the study. Basic principles and procedures were adapted from previous research (Fort et al., 2012; Jordan et al., 2005; Piecha et al., 2014; Torvinen, Kannu, et al., 2002; Torvinen, Kannus, et al., 2002). WBV is followed by a 20-min period of DNS training, including specific movement exercises according to the DNS approach accompanied by breathing, coordination, mobility

and stability core exercise and routine suggested in previous studies (Frank et al., 2013; Kobesova & Osborne, 2012; Mahdieh et al., 2020; Marinkovic et al., 2022). During the experiment, the MIX intervention group performed three training sessions weekly.

Control group (CONTROL)

The control group did not exercise or use any training intervention or other habitual training during the past two months. During this period, the control group maintained their regular daily routines without any modifications. They refrained from engaging in any form of physical activity or participating in training programs that could influence their fitness levels.

Statistical analyses

G*power 3.1 power analysis software (Heinrich-Heine-University, Düsseldorf, Germany) estimated the minimum total sample size ($N=140$) given the critical $F_{(3, 136)}=2.67$, an effect size $f=0.14$ (partial $\eta^2=0.02$), $p=0.05$, $1-\beta=0.80$, groups=4, time points=2, and correlation among the measurements=0.50. The authors presented data as means and 95% confidence intervals [95% CIs]. The Kolmogorov-Smirnov, Leven's, Box's, and Mauchly's tests confirmed the assumptions of normality, homogeneity of variances and covariances, and sphericity, respectively. General linear models (twelve separate 2x4 mixed-design analyses of covariances for each PS measure) estimated whether mean changes [95% CIs] in PS measure from initial to final testing depended on whether participants received the DNS, VIBRO, and MIX exercise program or did not (CONTROL) after controlling for mean-centered BMI (Cibulková et al., 2022; Hue et al., 2007). Following the time-by-group interaction effects, which revealed whether estimated changes over time depended on the participants' group (i.e., differed at least between one group-comparison pair), we computed simple effects tests to estimate mean changes over time (mean difference from initial to final testing) within the groups. The follow-up investigation proceeded with contrast analysis, which assessed the degree to which estimated mean changes of PS measures differed between the group-comparison pairs. The authors calculated the effect size for time-by-group interaction effects and simple effects using partial eta squared (partial η^2 : 0.01 small; 0.06 medium; 0.14 large) (Cohen, 2013) and Hedge's g average (Hedge's s_{av} : $<|0.20|$ trivial; $|0.20|$ small; $|0.50|$ medium; $|0.80|$ large) (Lakens, 2013), respectively. The Bonferroni test corrected p-values and 95% CI; the alpha level was $p\leq0.05$. We used SPSS version 23.0 (SPSS Inc., Chicago, IL, USA) and GraphPad Prism version 8.0 (GraphPad Software, San Diego, California, USA) to analyse and plot the data, respectively.

References

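### The fixed two-occasion ANCOVA by default compares completers: 53 of 230 randomised participants (23.0%) are absent from the final sample, and the plan does not test how far this could shift the group contrasts

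*Protocol*

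**What the plan says.** Protocol, Detailed Description, Participants: the sample was "divided using stratified randomisation into the MIX group (n = 58), DNS group (n=57), VIBRO (n=57), and CONTROL group (n=58"). The same paragraph then reports that "At the end of the experimental program, the final sample was 180 (MIX=45; DNS=45; VIBRO=44; CONTROL=43"). It gives no reason for any loss, overall or by arm. It also opens by saying that "The randomised, controlled interventional trial enrolled a gender-balanced group of 180 healthy young participants", so the number called enrolled is the number at the end and not the 230 randomised.

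Protocol, Testing procedures: there are two test occasions. "Initial testing was conducted on 20.4.2022 and final on 25.6.2022".

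Protocol, Statistical analyses: the model is fixed. "General linear models (twelve separate 2x4 mixed-design analyses of covariances for each PS measure) estimated whether mean changes" from the first to the second test depended on group, with adjustment for mean-centred BMI, in SPSS. The section names no analysis population and no handling of a missing final test. The sample size paragraph "estimated the minimum total sample size ($N=140"; dropout is not mentioned there.

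**The concern.** With two occasions, the time-by-group interaction in a mixed-design general linear model is a comparison of mean change between groups. A person with only one test has no change score, and the SPSS general linear model procedure drops that person by default. The description of the sample points the same way, because the enrolled number equals the final number.

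Randomisation protects the comparison of everyone assigned. It does not protect the comparison of those who stayed. More than a fifth of each arm is absent, and the arms asked different things of people: three had supervised sessions of rising difficulty, while CONTROL had to avoid training. Those who left one arm may therefore differ from those who left another even when the percentages match. At stake is whether the contrasts estimate the effects of the modalities in the people randomised, or only in those who finished.

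**Working it through.** **The plan's own sample size.** Inputs from Statistical analyses: f = 0.14 (partial eta squared 0.02), alpha 0.05, power 0.80, 4 groups, 2 time points, correlation r = 0.50. For the within-between interaction, lambda = N × f² × m / (1 − r), with 3 and N − 4 degrees of freedom.
- N = 140, f = 0.14: lambda = 140 × 0.0196 × 2 / 0.5 = 10.98, critical F(3,136) = 2.67, power 0.790.
- Taking f from eta squared, sqrt(0.02/0.98) = 0.1429, the minimum is 138, which becomes 140 in four equal arms. The stated figure is reproduced.
- With 177 analysed, power at f = 0.14 is 0.886. The loss does not bring power below plan, so the question is bias.

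**Loss by arm.** Inputs: the two sets of arm counts in Participants.

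| Arm | Randomised | Final | Absent | % |
|---|---|---|---|---|
| MIX | 58 | 45 | 13 | 22.4 |
| DNS | 57 | 45 | 12 | 21.1 |
| VIBRO | 57 | 44 | 13 | 22.8 |
| CONTROL | 58 | 43 | 15 | 25.9 |
| Total | 230 | 177 | 53 | 23.0 |

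With the stated total of 180, loss is 50/230 = 21.7%. The three training arms together lose 38/172 = 22.1%. A chi-square test across arms gives 0.40 on 3 df, p = 0.94.

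**Scale.** SD is the between-person SD at one test. SD of change = SD × sqrt(2 × (1 − 0.50)) = 1 SD. With about 44 per arm, the SE of a two-arm contrast of change is sqrt(2/44) = 0.213 SD. This ignores BMI adjustment and the Bonferroni correction.

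**Bias if only training-arm leavers differ.** Overstatement = proportion lost × gap, where the gap is how much less leavers would have changed than completers. The gaps are assumptions. Coverage = Phi(1.96 − b) − Phi(−1.96 − b), with b = bias/SE.

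| Gap (SD) | Overstatement (SD) | b | Coverage of a 95% CI |
|---|---|---|---|
| 0.25 | 0.22 × 0.25 = 0.055 | 0.26 | 94% |
| 0.5 | 0.22 × 0.5 = 0.11 | 0.52 | 92% |
| 1.0 | 0.22 × 1.0 = 0.22 | 1.03 | 82% |

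For comparison, suppose all three training arms gain d over CONTROL. Then lambda/N = (3/16) × d², and the planned value is 0.0196 × 2 / 0.5 = 0.0784. So d = sqrt(0.0784 × 16/3) = 0.65 SD, and the overstatements are about 9%, 17% and 34% of it.

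**Bias if leavers in every arm have the same gap.** (0.221 − 0.259) × gap = −0.038 × gap, or −0.01, −0.02 and −0.04 SD. This is negligible and runs against training.

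**What a likelihood-based model repairs.** With equal SDs and r = 0.50, expected change falls by 0.5 SD for each SD of initial score. If leavers in an arm start k SD away from its completers, the complete-pair mean change in that arm is off by 0.5 × proportion lost × k.
- Training arms only: k = 0.5 gives 0.5 × 0.221 × 0.5 = 0.055 SD, and k = 1.0 gives 0.11 SD.
- Opposite patterns in training and CONTROL, k = 0.5: 0.5 × (0.221 + 0.259) × 0.5 = 0.12 SD.

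Simulation of loss that depends on the initial score differently by arm gave complete-pair biases of about 0.06 to 0.16 SD. The likelihood model removed them, with a slightly smaller SE. Where the gap is unrelated to the initial score, simulation with 13/57 and 15/58 lost gave the same bias under both models: 0.056, 0.113 and 0.226 SD.

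**The case against.** The strongest reply is that the protocol nowhere says non-completers are excluded. Dropping incomplete pairs is a software default, imputation before the model is not ruled out, and analysis sets and missing-data rules are often left to an SAP, which is not shown here. This stands in part: a completers analysis is inferred from the model, the two occasions and the description of the sample. But the model itself is fixed in the protocol, and as written it can use only people with both tests.

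Second, loss is almost equal across arms and highest in the untrained arm. This also stands. Equal rates do not prove equal reasons, but they give no sign of training-related withdrawal. Setting the gap to zero in CONTROL is one-sided, since being told to avoid activity could also cause people to leave, and an equal gap leaves almost no bias.

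Third, a likelihood model does not remove bias from a gap unrelated to the initial score. That is correct, and it is why the shift analysis is needed as well.

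Fourth, not all 230 may have had an initial test, and the text does not say when the 53 left. That limits who can be added to the model and should be reported.

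A reader might go further and infer that people left because training injured or did not suit them, and that any record of harm was lost with them. The document does not support this. It gives no reasons for loss, it does not say that no other records exist, a figure in that section is not shown, and it makes no tolerability claim.

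**Conclusion.** The point holds as a weakness of the fixed analysis and should be corrected. Between 21.7% and 23.0% of those randomised are absent from the final sample, and the stated model by default compares the rest.

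Bias in favour of training is possible but not shown. Its size depends on an assumption that the document cannot settle: roughly 0.06 to 0.22 SD if only training-arm leavers would have done worse by 0.25 to 1.0 SD, and close to zero if leavers were alike in all arms. Interval coverage is materially affected only towards the upper end, at about 82% for a 1.0 SD gap. The figures rest on the protocol's correlation of 0.50, equal SDs at the two tests and about 44 analysed per arm. Power is not affected in any way that matters. No conclusion about harm or tolerability follows.

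**What to change.** In Statistical analyses, replace the complete-pair general linear model with a likelihood-based repeated-measures mixed model (SPSS MIXED). It should include all randomised participants who have an initial test, in their assigned arm, with the same time, group and BMI terms. Keep the completers analysis as a sensitivity analysis.

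This model corrects only for loss explained by the initial score and covariates. Therefore add a sensitivity analysis that shifts the missing final values in the training arms, in the unfavourable direction, by stated amounts such as 0.25, 0.5 and 1.0 SD. Report whether each contrast survives.

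In Participants, reconcile 180 with 177, and the 180 called enrolled with the 230 randomised. State by arm how many had an initial test. A table of reasons for loss by arm, with unknown allowed, would be useful reporting, but the point does not depend on it.

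The cost is small: the software is already named and no new measurements are needed. The downside is slightly more analysis, and results that may look less favourable under the shifts.

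### N=140 is said to give 80% power for a partial η² of 0.02, but on the scale SPSS reports for the interaction its power for 0.02 is about 25%

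*Protocol*

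**What the plan says.** The Statistical analyses section of the protocol reports a G\*Power 3.1 calculation that "estimated the minimum total sample size ($N=140$) given the critical $F_{(3, 136)}=2.67", with the remaining inputs given as "an effect size $f=0.14$ (partial $\eta^2=0.02$), $p=0.05$, $1-\beta=0.80$, groups=4, time points=2, and correlation among the measurements=0.50". The degrees of freedom (3, 136) identify the test as the time-by-group interaction in a design with four groups and two time points. The G\*Power effect-size option is not named, and no source is given for 0.02.

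The same section then states how results will be expressed: "The authors calculated the effect size for time-by-group interaction effects and simple effects using partial eta squared", read against cut-offs of 0.01 small, 0.06 medium and 0.14 large. The analysis software is SPSS 23.0. One term, partial η², is thus used for both the planning value and the reported value of the same interaction.

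**The concern.** G\*Power's default repeated-measures option and SPSS define the interaction effect size against different variances. The default f is scaled to the full within-cell standard deviation at a single time point, and the program applies the correlation afterwards. SPSS partial η² is the effect sum of squares divided by effect plus error sums of squares. Its error term is the within-person one, so the correlation is already in it. Converting a partial η² of 0.02 with f = √(η²/(1−η²)) and entering the result on the default scale counts the gain from the correlation in a place where it does not belong.

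A reader who compares 0.02 with the protocol's cut-offs will conclude that the trial had 80% power for a small effect. If the design was really powered for a medium one, a null interaction in any of the twelve models, or a finding of no difference between modalities, carries much less information than the document implies.

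**Working it through.** **Inputs** (protocol, Statistical analyses): N=140; critical F(3,136)=2.67; f=0.14, equated with partial η²=0.02; α=0.05; power 0.80; k=4 groups; m=2 time points; ρ=0.50. From the Participants section: group sizes at the end of 45, 45, 44 and 43, which sum to 177, against a stated total of 180.

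**Method.** Noncentral F with df1 = (k−1)(m−1) = 3 and df2 = (N−k)(m−1) = N−4.

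**Step 1: reproduce N=140.** On G\*Power's default scale λ = f²·N·m/(1−ρ) = 4f²N.

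- f = √(0.02/0.98) = 0.1429: at N=136 power is 0.795. At N=140, λ = 4 × 0.02041 × 140 = 11.43, critical F is 2.671 and power is 0.808. The smallest equal-group size reaching 80% is 140, as stated.
- f = 0.14 as rounded: at N=140, λ = 10.98 and power is 0.790; 80% needs N=144.

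So N=140 comes from converting 0.02 directly to f. The alternatives tried do not reproduce it:

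| Scale | N for 80% power |
|---|---|
| Default, λ = 4f²N | 140 (144 with f=0.14) |
| No correlation term, λ = 2f²N | 272 (284) |
| Between-groups test | 405 (422) |
| 0.02 as the interaction's own partial η² | 540–544 (564–568) |

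**Step 2: convert the powered effect to the reported scale.** With two time points the interaction test is a one-way comparison of change scores, whose variance is 2σ²(1−ρ). The squared effect size on that scale is f²·m/(1−ρ) = 4f², so

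partial η² = 4f²/(1+4f²).

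- f = 0.14: 0.0784/1.0784 = 0.073.
- f = 0.1429: 0.0816/1.0816 = 0.075.

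**Step 3: power for a partial η² of 0.02 on the reported scale.** Here λ = [0.02/0.98]·N, or ·(N−4) under the SPSS convention.

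| N | λ | Power |
|---|---|---|
| 140 | 2.78–2.86 | 0.249–0.256 |
| 177 | 3.53–3.61 | 0.313–0.319 |
| 180 | 3.59–3.67 | 0.318–0.324 |
| 540–544 | 11.02 | 0.80 |

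The partial η² detectable with 80% power is about 0.074 at N=140 and about 0.059 at N=177 (0.076 and 0.061 under the N−4 convention).

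**Step 4: check by simulation.** Change scores, 35 per group, 20,000 runs: population partial η² 0.02 gives power 0.255; f=0.14 on the default scale gives 0.790.

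**Step 5: a rough check from the protocol's own critical F.** F(3,136)=2.67 corresponds to an observed partial η² of 3×2.67/(3×2.67+136) = 0.056. An observed 0.02 gives F = (0.02/0.98)×136/3 = 0.93, p=0.43. Observed partial η² is biased upward (mean about 0.041 in the simulation when the population value is 0.02), so this only illustrates the conflict. The noncentral F result in Step 3 carries the point.

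**The case against.** The best defence is that nothing is miscalculated. On G\*Power's default scale N, critical F, f and power all agree, and f=0.14 does correspond to 0.02 through f²/(1+f²). If f=0.14 was meant only on that scale, N=140 has about 80% power, and at 177 to 180 completers it has 0.89–0.90. The protocol does not say that 0.02 is an SPSS value and never calls the planning effect small. Estimates come with 95% confidence intervals, which show directly what is excluded. The training ended in June 2022, so neither enrolment nor the analysis would change.

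Much of this stands. The fault is one of scale, the 25% applies to the effect as SPSS will report it, and the intervals are the better guide to what the data rule out. But the defence does not rescue the sentence. That N=140 follows from 0.1429 and not from 0.14 shows that 0.02 was the starting value. The section gives that value the same name as the interaction effect it reports later, with cut-offs alongside, and nowhere warns that the two differ nearly fourfold. On either reading, 0.02 cannot stand beside 80% power on the scale the reader is given.

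The BMI covariate does not alter this. It costs one degree of freedom (power 0.2404 against 0.2405 with f=0.14). How much variance in change it explains is not stated; reaching 80% at N=140 would require the error variance to fall to roughly a quarter.

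**Conclusion.** The concern holds. As an interaction partial η² of the kind the protocol reports, 0.02 is detected with about 25% power at N=140 and 31–32% at the analysed 177 to 180, not 80%. The design is powered for about 0.073 to 0.075 at N=140 and about 0.06 at the analysed N, a medium effect by the protocol's own cut-offs.

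This rests on ρ=0.50 and two time points as stated, α=0.05 for each omnibus test, equal groups, and no variance in change explained by BMI. Use of G\*Power's default option is inferred, but it is the only scale tried that reproduces N=140. The total of 140 is itself sound on that scale; the pairing of 0.02 with 80% power is what is wrong.

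**What to change.** Delete the parenthetical partial η² of 0.02 and restate the sample-size sentence, for example: *A total of 140 participants gives about 80% power for f=0.14 on G\*Power's default repeated-measures scale (four groups, two time points, ρ=0.50), equivalent to a time-by-group partial η² of about 0.07 as reported by SPSS, a medium effect.*

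Add that at the analysed N the interaction partial η² detectable with 80% power is about 0.06, and that power for 0.02 is about 0.3, so that null interactions are not read as excluding small effects. Interpretation of null results should rest on the confidence intervals.

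The cost is a sentence or two of the protocol and a less favourable stated detectable effect. Enrolment, model and analysis are unchanged.

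### Twelve unranked primary interaction tests share a Bonferroni sentence that names no family, so either the primary error is uncorrected or the stated 80% power does not hold per outcome

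*Protocol*

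**What the plan says.** Under Testing procedures, the protocol lists sway area, centre-of-force path, and then "Medio-Lateral (ML) displacement (mm), and Anterior-Posterior (AP) displacement (mm) as primary outcomes", for single- and double-leg stance. No outcome is ranked above another. The same section says of the single-leg test that "The order of testing between the left and right legs was randomised", so both legs were measured.

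Under Statistical analyses, the models are described as "General linear models (twelve separate 2x4 mixed-design analyses of covariances for each PS measure". The programme effect is read from the time-by-group interaction in each model. Simple effects within groups come next, and then: "The follow-up investigation proceeded with contrast analysis, which assessed the degree to which estimated mean changes of PS measures differed" between pairs of groups. After the effect-size conventions comes the only sentence on multiplicity: "The Bonferroni test corrected p-values and 95% CI; the alpha level was" 0.05. It gives neither a family nor a divisor.

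The sample size in the same section is N=140, "given the critical $F_{(3, 136)}=2.67", with f=0.14 (partial eta squared 0.02), alpha 0.05, power 0.80, four groups, two time points and a correlation of 0.50 among the measurements.

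Under Participants, "the final sample was 180 (MIX=45; DNS=45; VIBRO=44; CONTROL=43"). The listed arms add to 45 + 45 + 44 + 43 = 177.

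**The concern.** A Bonferroni correction fixes a threshold only once its family is known. Here two readings are open, and each conflicts with something the protocol needs.

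- **Follow-ups only.** The simple effects and contrasts are corrected within each model. The twelve interactions, which decide whether a programme affected a primary outcome, are each judged at 0.05 with no correction across outcomes.
- **Across the twelve outcomes.** The primary error is controlled, but the sample size was worked out for one test at 0.05, so the stated 80% power does not describe any single outcome.

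A reader of a result such as p = 0.02 for one interaction cannot tell whether it meets the trial's own criterion.

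**Working it through.** **1. Which reading the text favours.** Three features point to follow-ups only. The sentence stands after the simple effects, the contrasts and their effect sizes. It corrects p-values together with 95% confidence intervals, which belong to mean changes and contrasts; a 3-df omnibus F has no such interval. The sample size uses the unadjusted critical value (step 2). None of these is conclusive.

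**2. The protocol's own figure.** For a within-between interaction with k = 4 groups and m = 2 time points, df = 3 and N − 4 = 136, and lambda = f² × N × m/(1 − rho).

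- Critical F(3,136) at 0.05 = 2.671, which matches the stated 2.67. At 0.05/12 = 0.00417 it would be 4.614.
- f = 0.14: lambda = 0.0196 × 140 × 2/0.5 = 10.976, power 0.790.
- f = √(0.02/0.98) = 0.1429: lambda = 11.429, power 0.808.

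The stated N=140 for 80% power is therefore reproduced, as the size for one test at 0.05.

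**3. Follow-ups-only reading.** The expected number of false-positive interactions under no effect is 12 × 0.05 = 0.60, whatever the correlation. If outcomes are independent, the chance of at least one is 1 − 0.95^12 = 0.460. This is a ceiling, because parameters from one stance share recordings. The protocol gives no correlation between outcomes, so the values of r below are assumptions. The error figures come from simulated F tests on change scores with arms of 45/45/44/43 and without the BMI covariate. The last column also requires at least one of the six pairwise contrasts, Bonferroni-corrected within that model, to be significant.

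| Assumed correlation | At least one false interaction at 0.05 | Same, at 0.05/12 | False interaction at 0.05 plus a corrected contrast |
|---|---|---|---|
| 0 | 46% | 4.8% | 38% |
| 0.3 | 40% | 4.4% | – |
| 0.5 | 33–34% | 4.1% | 28% |
| 0.7 | 25% | 2.9% | – |
| 0.8 | 20% | 2.4% | 16% |
| 0.9 | 14% | 1.6% | 12% |
| 0.8 within stance, 0.3 between | 30% | – | 24% |
| 0.8 within, 0.5 between | 27% | – | 21% |
| 0.9 within, 0.5 between | 23% | – | 19% |

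The simulation error is about half a percentage point or less in the first two error columns, and the last column should be read to within a point or two.

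**4. Across-outcomes reading.** The same noncentral F at 0.05/12 gives the power per outcome:

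| N | f = 0.14 | f = 0.1429 |
|---|---|---|
| 140 (planned) | 0.457 | 0.482 |
| 177 (sum of listed arms) | 0.616 | 0.643 |
| 180 (stated final sample) | 0.628 | 0.655 |

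For 80% power per outcome at 0.05/12, about 236 participants would be needed (228 with f = 0.1429).

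**5. The count of twelve.** The protocol states twelve models but does not list them. Four parameters × left, right and double leg = 12 is an inference. If only eight outcomes (4 × 2) were meant, the uncorrected error would still be 34% if independent and 26% at r = 0.5.

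**The case against.** The strongest reply is that the sentence is unclear rather than wrong. It does not limit Bonferroni to the follow-ups, and if it spans the twelve outcomes the error is sound. That stands. A reader might infer that the primary analysis is shown to be uncorrected; the text favours this but does not establish it.

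A reader might also infer a single error rate of about one in three, because 0.50 appears in the sample size. That 0.50 is the correlation over time within a person, not between outcomes. Outcomes from the same recording are probably more alike than outcomes from different stances, so the 23–30% rows are at least as plausible, and only a range can be defended.

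Nor is a false interaction free of any check. On the follow-ups-only reading, a claim that one group did better than another must also pass a corrected contrast in the same model. This lowers the range to about 12–38%, still well above 5%. The protocol also states no rule that one positive outcome out of twelve makes the trial a success; it does not exclude one either.

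Finally, a statistical analysis plan might name the family. This protocol, however, sets out the models, alpha, follow-ups and correction itself, so the ambiguity lies in what it states and not in something it leaves for later.

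**Conclusion.** The point holds as an ambiguity with consequences on both sides and should be fixed. On the favoured reading, twelve primary interactions are each tested at 0.05: 0.6 false positives are expected under no effect, and the chance of at least one is about 14–46% for an assumed correlation of 0.9 down to 0. On the other reading the familywise error is at most 5%, but the power per outcome is 46–48% at N=140 and 62–64% at N=177.

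The power figures rest on the protocol's own effect size and correlation over time. The error figures rest on assumed correlations between outcomes and on twelve primary outcomes, whose make-up is inferred. The documents do not support the stronger statement that the trial's false-positive rate is known to be inflated by a given amount.

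**What to change.** In Statistical analyses, state that the twelve time-by-group interaction p-values form one family, Bonferroni-corrected at 0.05/12 (p at most 0.0042), and that simple effects and contrasts are additionally corrected within each model. Report all estimates and confidence intervals, claim a programme effect only for outcomes whose interaction passes, and label the rest exploratory. There is no need to withhold follow-up estimates.

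State that the 80% power applies to one test at 0.05, and give the power per outcome at 0.05/12: 46–48% for N=140 and 62–64% for N=177.

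Keep all outcomes primary. The protocol records that "Initial testing was conducted on 20.4.2022 and final on 25.6.2022" and that outcomes were not changed once the trial had started, so ranking them now would invite selection by result. Single-step Bonferroni is the method already named, and over the twelve interactions it cannot make a further interaction significant on either reading.

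The cost is a few sentences, with no new data or model. The threshold per outcome is stricter and the stated power lower. The correction is conservative when outcomes are highly correlated (actual familywise error about 1.6% at r = 0.9), and contrasts remain controlled only within each outcome.
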